**STAGE 2 RCT – Secondary Aims:**

(4a) *Examine LDX and CBT effects, alone and in combination, for longer-term BED outcomes. Our two-stage design will allow comparison of CBT (i.e., Stage 1 CBT-only short-term) versus the Stage 2 LDX/placebo maintenance treatment (i.e., Stage 2 LDX/placebo following Stage 1 LDX or Stage 1 CBT+LDX) for longer-term outcomes through 18 months.* This will inform clinical questions regarding whether LDX maintenance treatment following either acute LDX treatment or acute combined CBT+LDX differ and whether it offers any additional benefits over acute CBT-only.

(4b) Among *Non-responders* to Stage 1 acute treatments with LDX (i.e., LDX and CBT+LDX), *explore the effectiveness of switching to an alternative medication NB vs placebo* for primary outcomes (reducing binge-eating and reducing weight) and secondary outcomes (binge remission, ED pathology, depression).

(5) Secondary Aims: Generate *cost-effectiveness* estimates of treatments. Incremental cost effectiveness ratios (ICERs) will be computed for LDX vs CBT and LDX+CBT vs CBT (using quality-adjusted life years).

2. **Probable Duration of Project:** State the expected duration of the project, including all follow-up and data analysis activities.

September 1, 2018- August 31, 2025

3. **Background:** Describe the background information that led to the plan for this project. Provide references to support the expectation of obtaining useful scientific data.

**SIGNIFICANCE:** Obesity (OB) is an increasingly prevalent, refractory, and serious public health problem, with estimates that 34% of U.S. adults are obese (Flegal, Carroll et al. 2010). Obesity is considered one of the most serious public health problems of the 21st century. Economic consequences of OB are staggering; associated annual medical costs were estimated at \$147 billion (roughly 10% of all medical spending) (Finkelstein et al. 2009), which reflects continued escalation since estimates of \$75 billion five years earlier (Finkelstein et al.

2004). This study focuses on testing treatments for a high-risk subgroup with binge-eating disorder (BED) (Hudson, Hiripi et al. 2007; Kessler et al., 2013).

Binge Eating Disorder (BED) – An Important Clinical Subgroup of Persons with Obesity

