**Pre-Screening:** Participants responding to recruitment efforts (see pages 35-36) will be screened by telephone. If participants prefer to answer some of the screening questions through the Yale Qualtrics system, participants will indicate their consent to the recruitment/screening process in the online system. Potentially eligible participants will be consented and evaluated in-person by trained supervised research clinicians (doctoral level and/or advanced trainees). Participants will complete survey measures of eating behaviors and psychopathology and psychosocial functioning around the time of the in-person appointment.

[figure not shown]
Participants who provide informed consent and are determined to be eligible (see page 15-16) will then participate in the study as depicted and described in the following paragraphs. See also Figure 1 (page 8).

**Stage 1**, N=180 patients with BED and obesity will be randomized to one of three 12-week treatments: CBT, LDX, or CBT+LDX.

**In Stage 2**, patients who received pharmacotherapy (Stage1 LDX or CBT+LDX) and were “Responders” (defined as 65% or more decrease in binge eating) will be randomly assigned in equal proportions (blocked randomization stratified by first treatment) to LDX or placebo (double blind) for 12 weeks.

“Non-responders” to Stage 1 pharmacotherapy (LDX or CBT+LDX) will be randomized to a second medication (NB or placebo) in double-blind fashion for 12 weeks. Stage 1 CBT patients will be followed without further treatment; this will allow controlled comparison of Stage 1 RCT and context for Stage 2 RCTs.

Independent assessments will determine outcomes after discontinuation of treatments through 18 months. Secondary aims are to produce important new data regarding predictors of outcomes and moderators of treatment effects to inform prescription (i.e., for whom LDX vs. CBT work best), and exploration of potential mediators through which the distinct treatments achieve outcomes, and cost-effectiveness estimates.

**Figure 1.** Study design

Potential participants will be screened by telephone and potentially eligible patients will be consented and evaluated in-person by trained supervised research clinicians (doctoral level and/or advanced trainees). (see page 36).

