**Randomization to Stage 2 Treatments for LDX and CBT+LDX (Stage 1) “Responders”.**

“Responders” to Stage 1 LDX (i.e., LDX and CBT+LDX) treatments will be defined as 65% or greater reduction in binge-eating. This cut-point is based on reliable findings regarding prognostic significance of such reductions ([name] et al., 2006; 2012) and supported by recent report on “time course of the effects of LDX” (McElroy et al., 2017). “Responders” will be randomized in equal proportions (using stratified blocked randomization with Stage 1 treatment as a stratifying variable) to LDX or placebo (double-blind) for 12 weeks.

**CBT Treatment Protocol.** CBT will be delivered by trained and monitored research clinicians following manualized protocols we have used successfully in previous RCTs (e.g., [name] et al., 2005, [name] et al., 2011). CBT will be delivered in individual sessions weekly for 12 weeks following CBT manuals based on Fairburn et al (1993) used in our RCTs ([name] et al., 2005, 2011) which are similar to those used in major RCTs testing CBT delivered via 12-24 weeks (Wilfley et al., 2002; Wilson et al., 2010). The CBT manuals provide detailing session-by-session procedures for clinicians and parallel guides are provided to the patients to facilitate homework and mastery of the material. CBT, a specialist focal treatment, consists of

three overlapping phases. Phase one involves establishing a collaborative therapeutic relationship while focusing on educating the patient about the nature of binge-eating and factors thought to maintain the problem. Specific behavioral strategies (e.g., self-monitoring) are used to help patients identify problematic eating patterns while establishing a normal structured eating pattern. Phase two integrates cognitive restructuring procedures, where patients learn to identify and challenge maladaptive cognitions regarding eating and weight/shape and thoughts that trigger binge-eating. Phase three focuses on maintenance of change and relapse prevention.

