20. For Stage 2 non-responders only, history of anorexia nervosa or history of bulimia nervosa will be exclusionary for that stage; however, history of anorexia nervosa or history of bulimia nervosa will not exclude individuals from Stage 1, Stage 2 "Responder" treatment (LDX), or any of the follow-ups."

21. For Stage 2 non-responders only, history of allergy or sensitivity to bupropion or naltrexone will be exclusionary for that stage; however, history of allergy or sensitivity to bupropion or naltrexone will not exclude individuals from Stage 1, Stage 2 "Responder" treatment (LDX), or any of the follow-ups.
22. Non-responders, during Stage 2, currently taking Tramadol or opioid pain medications or drugs.

9. How will **eligibility** be determined, and by whom?

Participants will be interviewed by a trained research clinician (MINI and EDE) to determine whether they meet criteria for binge-eating disorder. These diagnostic clinical interviews will also determine whether participants have any co-existing psychiatric conditions (including substance use disorders) that require hospitalization or more intensive/different treatment. The study physician will determine medical eligibility based on results of participants' physical examination (within one year of starting the study), as well as results of the baseline assessment. Information obtained from the physical examination will include an EKG and a list of current medications, which participants will be asked to bring to their baseline assessment. For otherwise healthy participants, an EKG during the past two years will be acceptable. Medical review is required for all participants. Therefore, communication with treating physicians occurs for each patient. If the study physician requires additional information, the study physician will contact the treating physician.

Source of Research Materials

Data will be collected in the form of standardized clinical interviews, self-report questionnaires, clinical interviews, and traditional medical methodologies including standard laboratory blood tests. All the assessments are described in the previous section (Research Design). The data will be used for clinical and research purposes only.

10. **Risks:** Describe the reasonably foreseeable risks, including risks to subject privacy, discomforts, or inconveniences associated with subjects participating in the research.

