### DATA ANALYSIS

Baseline demographic and clinical characteristics for randomized groups will be compared using chi-square tests for categorical variables, and ANOVA or Kruskal-Wallis tests for continuous variables. Continuous variables will be examined for adherence to normal distribution using normal probability plots and Kolmogorov-Smirnov tests. If normality not satisfied and transformations do not help with achieving normality, alternative analytic strategies will be considered such as generalized estimating equations or nonparametric methods. Dropouts and completers will be compared. Analyses will be intent-to-treat; patients will be followed regardless of treatment completion to minimize missing data. Primary outcomes will be tested at two-sided 0.05 significance level. Secondary analyses will be adjusted for multiple tests using Bonferroni correction.

Overall Data Analysis Strategy will involve MIXED EFFECTS MODELS (Diggle et al, 2002, Gueorguieva & Krystal, 2004) to compare treatments. These models allow for different numbers of observations per subject, use all available data on each subject, and are unaffected by randomly missing data. Further advantage is capacity to test and account for individual-difference contributions to treatment outcomes (Cudeck, 1996; Cudeck & Klebe, 2002; Hedeker et al., 1996; Hedeker & Gibbons, 1996; Singer, 1998). They provide flexibility in modeling the correlation structure of data. In models for each outcome, we will include fixed effects of time, treatment, and interaction between time and treatment, and random subject-level effects. Because we cannot a priori predict the shape of responses over time in each arm of the trial we will first treat time as a categorical predictor and will then test for polynomial trends over time. We will consider different error structures (e.g., AR1, independence) and select the best fitting one based on information criteria. We will

compare dropout patterns between groups and if there are concerns of informative dropout or informative intermittent missing data, we will use pattern mixture models (Hedeker & Gibbons, 1997) to perform sensitivity analyses.

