(1) **STAGE 1 – Primary Outcomes Aim 1 and Secondary Outcomes Aim 2a:** Compare LDX and CBT effects, alone and in combination, for acute BED outcomes. Analyses examining the co-primary outcomes (reduction in binge-eating and percent weight loss) and examining the secondary outcomes (binge remission, eating disorder psychopathology, depression, metabolic variables) will be intent-to-treat using mixed-effects models per the overall strategy described above. Mixed-model analyses on continuous (or pseudo-continuous) data will use SAS PROC MIXED; mixed-model analyses on binary variables will use SAS PROC GLIMMIX. Logistic regression will be used for categorical outcomes (i.e., remission from binge-eating (defined as 0 binges/past 28 days on EDE interview). Significantly greater reductions in binge eating in CBT and CBT+LDX groups compared to LDX, and weight loss in LDX and CBT+LDX compared to CBT will be considered supportive of our primary aim hypotheses. We do not anticipate significant differences between CBT and CBT+LDX on binge eating and between LDX and CBT+LDX on weight loss but the mixed model approach will allow us to estimate the magnitude of the effects with associated confidence intervals.

(2) **STAGE 1 – Secondary Outcomes Aim 2b:** Explore conceptually and empirically supported predictors, moderators, and mediators for the primary outcomes (reductions in binge-eating and weight loss) and secondary categorical outcome (binge-eating remission). We will use the Kraemer et al (2002) approach to assess predictor, moderator and mediator effects by adding potential predictor, moderator and mediator variables to the models above. Predictors will be identified as variables with significant main effects on the outcome, moderators as variables with significant interactions with treatment on the outcome, and mediators will need to be significantly affected by treatment, to be related to the outcome and have main or interactive effects with treatment on the outcome. We will explore two empirically-supported predictors and moderators of BED outcomes – overvaluation of shape/weight (EDE) and depression (BDI-II) ([name], Masheb et al., 2012; [name] et al., 2013). It is necessary to test previous findings to establish them specifically for CBT and LDX treatments to inform prescription (i.e., for whom these “leading” treatments work best).

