analytic strategy of studies testing medication for maintenance (i.e., fluoxetine) for bulimia nervosa (Romano et al (2002) and for anorexia nervosa (Walsh et al (2006) which was recently used in the Shire maintenance study of LDX for BED (Hudson et al., 2015). Stage 2 LDX and placebo will be compared on the proportion of Stage 1 responders who “relapse” using chi-squared tests and Cox Proportion Hazards Tests; we will explore further using survival analyses to estimate whether time to relapse differs between LDX and placebo. For the secondary outcomes, we will use mixed effects models to assess whether there is significant change in binge eating or weight loss between the group who continue LDX treatment and the group who receive placebo. We anticipate that subjects randomized to LDX maintenance will maintain better outcomes than patients randomized to placebo. We will also perform parallel analyses on all three groups (CBT, LDX, CBT+LDX) to compare outcomes at the 6-month time point (i.e., comparing 3-month CBT and 6-month two-stage treatments).

(4a) **STAGE 2 – Secondary Aim 1:** Explore LDX and CBT effects, alone and in combination, for longer-term BED outcomes. Our two-stage design will also allow us to also compare CBT (i.e., Stage 1 CBT-only short-term) versus the Stage 2 LDX/placebo maintenance treatment (i.e., Stage 2 LDX/placebo following Stage 1 LDX or Stage 1 CBT+LDX) for longer-term outcomes through 18 months. This will inform clinical questions regarding whether LDX maintenance treatment following either acute LDX treatment or acute combined CBT+LDX differ and whether it offers any additional benefits over acute CBT-only (4b).

**STAGE 2 – Secondary Aim 2:** Among Non-responders to Stage 1 treatments with LDX, Explore the effectiveness of switching to an alternative medication (NB versus placebo). Primary outcomes will be reducing binge-eating and reducing weight and secondary outcomes will be binge-eating remission, eating-disorder pathology, and depression. We will use similar analyses to Primary Aim 1: mixed models for the continuous outcome variables and logistic regression for categorical (remission) variable.

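### Aim 4a sets an unselected CBT arm against maintenance groups made up only of Stage 1 responders, which favours maintenance on binge-eating and can hide a CBT advantage

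*Combined protocol and SAP*

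**What the plan says.** Under Statistical Considerations, Data Analysis (4a), the plan will "compare CBT (i.e., Stage 1 CBT-only short-term) versus the Stage 2 LDX/placebo maintenance treatment", where maintenance follows Stage 1 LDX or CBT+LDX and outcomes run through 18 months. The Statement of Purpose gives the question to be answered: "whether LDX maintenance treatment following either acute LDX treatment or acute combined CBT+LDX differ and whether it offers any additional benefits over acute CBT-only".

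The two sides are formed differently.

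- **Maintenance.** Only participants on LDX or CBT+LDX with a reduction in binge-eating of 65% or more qualify. They "will be randomized in equal proportions (using stratified blocked randomization with Stage 1 treatment as a stratifying variable) to LDX or placebo". Non-responders go to NB or placebo instead.
- **CBT.** The Research Plan says "Stage 1 CBT patients will be followed without further treatment". It states no split by response.

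The Research Plan justifies the 65% cut-point by its prognostic value. For Stage 1, the plan counts as support for its hypotheses: "Significantly greater reductions in binge eating in CBT and CBT+LDX groups compared to LDX". The only all-arms analysis spelled out beyond Stage 1 is in Data Analysis (3): "We will also perform parallel analyses on all three groups (CBT, LDX, CBT+LDX) to compare outcomes at the 6-month time point".

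**The concern.** Maintenance membership depends on how a participant did in Stage 1, and it is judged on the outcome that will later be compared. LDX and CBT+LDX participants who did badly are removed from one side, while CBT participants who did badly stay on the other. On binge-eating this favours maintenance whenever early response predicts later outcome, which is the plan's own reason for choosing the cut-point.

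The general intent-to-treat statement does not help. A participant never re-randomised to LDX or placebo cannot belong to a maintenance group under any analysis principle.

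The plan says the comparison will inform whether LDX maintenance adds benefit over acute CBT. If CBT is better than LDX on binge-eating, as the plan expects, the selection can erase most of that difference at entry to Stage 2. If the arms are equal, it can create an apparent maintenance benefit.

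**Working it through.** **Inputs from the Power Analysis.** There are 60 participants per arm and 20% dropout. Remission is 62% or 64% with CBT and 40% or 36% with LDX. Response is 65–70%, giving about 80 responders from LDX and CBT+LDX and 64 after a further 20% dropout.

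**Plan figures reproduced.** Responders: 120 × 0.65 = 78 to 120 × 0.70 = 84 (stated: about 80). Completers: 80 × 0.8 = 64. Power at 32 per arm for relapse of 4% vs 32%, two-sided 0.05, exact enumeration of the uncorrected chi-square: 89.3% (stated: 89%). The plan gives no sample size or power for Aim 4a.

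**Step 1: remission among responders.** Zero binges is a 100% reduction, so every remitter is a responder and P(remission | response) = P(remission) / P(response). This assumes that the LDX remission and response rates describe the same sample.

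- Lowest: 0.36 / 0.70 = 0.514
- Highest: 0.40 / 0.65 = 0.615

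**Step 2: the CBT advantage over LDX.**

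- As randomised: 0.62 − 0.40 = 0.22 to 0.64 − 0.36 = 0.28
- Against LDX responders: 0.62 − 0.615 = 0.005 to 0.64 − 0.514 = 0.126
- If half of the selection shift persists (assumption): 0.112 to 0.203

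**Step 3: power to detect that advantage.** Pooled two-proportion z-test, exact binomial enumeration. Sample sizes after 20% dropout: 60 × 0.8 = 48 per arm as randomised; LDX responders 60 × 0.65 × 0.8 ≈ 31 to 60 × 0.70 × 0.8 ≈ 34.

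| Comparison | Two-sided 0.05 | Two-sided 0.0125 |
|---|---|---|
| CBT 48 vs LDX 48, as randomised | 59–80% | 35–59% |
| CBT 48 vs LDX responders 31–34 | 3–21% | 1–9% |
| Same, half of the shift persisting | 17–46% | 7–25% |

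The plan says "Secondary analyses will be adjusted for multiple tests using Bonferroni correction" but gives no number of tests; 0.0125 assumes four.

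**Step 4: arms truly equal.** Assume 38% remission and 67.5% response in every arm. Responders then show 0.38 / 0.675 = 0.563 against 0.38 for CBT. The table gives the probability of a significant result favouring maintenance.

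| Comparison | 0.05, full shift | 0.05, half shift | 0.0125, full shift | 0.0125, half shift |
|---|---|---|---|---|
| CBT 48 vs all maintenance 64 | 50% | 16% | 29% | 6% |
| CBT 48 vs LDX maintenance only 32 | 36% | 12% | 18% | 5% |

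Without selection, the chance in that direction at 0.05 is about 2.6%.

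**Step 5: CBT+LDX.** The plan anticipates no significant difference from CBT on binge-eating. If CBT+LDX remission equals that of CBT and its response rate is also 65–70% (both assumptions), its responders show 0.62 / 0.70 = 0.886 to 0.64 / 0.65 = 0.985. That is an apparent lead of 27–34 points over CBT with no true difference. Pooling LDX and CBT+LDX responders 1:1 gives maintenance an apparent lead of about 7–16 points, while the arms as randomised have CBT ahead by 11–14 (half of 22–28). If response to CBT+LDX is higher than 65–70%, these apparent leads are smaller.

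**The case against.** The strongest reply is that (4a) opens by naming LDX and CBT effects, alone and in combination, and presents the maintenance contrast as something the design also allows. With an intent-to-treat mixed-model strategy, assessments of all arms to 18 months and a three-group analysis at 6 months, a by-arm long-term comparison may be intended. That reading is possible, but no 18-month by-arm analysis is spelled out. The contrast that is spelled out is the selected one, and the 6-month analysis does not say how responders and non-responders are combined.

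Second, the aim is secondary and exploratory, and the Research Plan describes CBT follow-up as context for Stage 2. Aim 4a names no endpoint or test, so the remission test used here is ours. This stands and limits the severity.

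Third, the largest figures describe month 3, and the documents do not say how much of the selection shift survives to 18 months. This also stands. At a quarter of the shift, the false-benefit rate (48 vs 64, two-sided 0.05) is about 7%. The sample sizes are those at the end of treatment, and the equal-arms case ignores the relapse difference that the plan expects between LDX and placebo maintenance.

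Fourth, the remission and response rates come from different cited reports, so the ranges are illustrative. These points change the size of the bias. They do not remove the asymmetry.

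**Conclusion.** The concern holds and should be fixed. As worded, the maintenance-versus-CBT contrast through 18 months is not randomised, and on binge-eating its bias favours maintenance. At entry to Stage 2 the selection reduces an expected CBT advantage of 22–28 points to about 1–13. With half of the shift persisting, 11–20 points remain. With truly equal arms, the chance of a false maintenance benefit at 5% is about 50% with the full shift and 16% with half.

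These sizes rest on three assumptions: the LDX remission and response rates apply to the same sample, remission is the outcome tested, and the selection shift persists to the stated degree. The equal-arms figures also assume 38% remission and 67.5% response in every arm. No size is given for weight, because the documents do not relate binge response to weight loss. The comparison of LDX with placebo among re-randomised responders is unaffected.

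**What to change.** In Data Analysis (4a), specify that the longer-term comparison with CBT through 18 months is by Stage 1 randomised arm (CBT, LDX, CBT+LDX), keeping every participant whatever the response. State that it estimates the whole two-stage strategy, including the non-responder branch.

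Keep any maintenance-versus-CBT contrast as a supporting analysis, labelled non-randomised, with the CBT side restricted to participants who meet the same 65% criterion.

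Two additions are optional. If embedded regimes are to be estimated:

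- take inverse-probability weights from the actual allocation ratio in each branch (equal allocation is stated only for responders) and use robust standard errors;
- name the non-responder option that the regime follows;
- say how the analysis handles non-responders who cannot enter the NB/placebo comparison, since "For Stage 2 non-responders only, history of anorexia nervosa or history of bulimia nervosa will be exclusionary for that stage".

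It would also help to state how many tests the Bonferroni correction covers.

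The cost is wording and analysis time. Assessments of all arms to 18 months are already scheduled, so no visits or participants are added. The by-arm comparison answers a question about strategies rather than about maintenance alone, and weighted regime estimates would have wider intervals.
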